### Inclusion Criteria #2:

[figure not shown]
Surgical bioprostheses true ID was  $\geq$  19 mm and  $\leq$  27 mm and was confirmed by either CT or confirmed by the ViV Aortic App. Refer to the PCR website <https://www.pcronline.com/PCR-Publications/PCR-mobile-apps/Valve-in-Valve-Aortic-app>

Note: if CT was contraindicated and/or not possible to be obtained, a transesophageal echocardiogram (TEE) will be accepted for sizing.

## 8 SUBJECT ENROLLMENT

Patients must first meet all inclusion criteria and none of the exclusion criteria. Patients must also have had the Portico™ or FlexNav™ delivery system enter their body with the intent to implant the Portico transcatheter aortic valve via ViV procedure. In order for patients to be enrolled as study subjects, the above must be met and the subject (or legally authorized representative/next of kin) must sign the approved study ICF and any required forms designated by the study site/local/national authorities, based on geographic regulations. Patients deceased at the time of study screening may be enrolled per local and national regulations. The enrollment process is outlined below in **Figure 3**.

**Figure 3: Flowchart of Screening and Enrollment**

### 8.1 Point of Enrollment

Subjects will be considered enrolled into the study after completing the following:

- Signed Informed Consent is obtained (as applicable from the patient, legally authorized representative, or next of kin)
- The subject met all of the inclusion and none of the exclusion criteria for one of the study arms.
- Subject had the Portico™ or FlexNav™ delivery system enter his/her vasculature.
- If the subject is deceased, then all local and national requirements for consenting and/or enrollment must be met prior to enrollment and data collection in the study database.

If a patient is enrolled but then subsequently is found to not meet all eligibility criteria, the patient would be excluded and a Protocol Deviation CRF would be completed for not meeting eligibility. Patients who are deemed screening failures are not considered enrolled and are not part of the study analysis population.

The Principal Investigator or delegated study personnel will record enrollment information (name of the study, date of consent and inclusion/exclusion information) in the medical records and the screening/consent study database forms within one week of consenting. The Principal Investigator must document in the enrollment note that the patient met eligibility criteria and was deemed to be at increased risk for surgery to replace the original failed aortic surgical bioprosthetic valve.

Notification of subject enrollment to the Sponsor is considered to have occurred once the patient met all eligibility criteria, the required consent process and forms were completed (with documentation of enrollment in the medical records), and when the screening/consent study database forms have been completed.

## 8.2 Subject Lost to Follow-up and Withdrawal

Subjects must be informed about their right to withdraw from the study at any time and for any reason without sanction, penalty or loss of benefits to which the subject is otherwise entitled. Withdrawal from the study will not jeopardize the subject's future medical care or relationship with the study site Principal Investigator. Subjects will be requested to provide the reason for the request to withdraw from the study. The Principal Investigator must make all reasonable efforts to retain the subject in the study until completion of the study.

A study subject that has been withdrawn from the study will not be replaced. All data collected up to the point of their study withdrawal will be reported and included in the data analysis as applicable.

If a subject cannot be reached and review of their medical records does not provide sufficient information to assess the status and performance of their VIV, the site should make every effort to reach the subject and their local or referring physician. The efforts undertaken to contact the subject, referring physicians, including internists as well as cardiologists, family members, or other alternate contacts must be noted in the subject's records. These efforts must include at least two attempts of telephone contact on separate dates, and a registered letter before considering the subject lost-to-follow-up.

Reasons for early termination include, but are not limited to:

1. Subject refuses to continue participating in the study, withdraws consent
2. Subject is 'lost to follow-up': Site personnel should at all times make all reasonable efforts to locate and communicate with the subject in order to achieve subject compliance to the scheduled follow-up visits:
  - A subject will be considered 'lost to follow-up' after one missed visit, and a minimum of two phone calls from the investigational site to the subject or listed contact of the subject. These two phone calls need to be documented in the subject's hospital records.
  - If these two attempted phone calls are unsuccessful, a letter should be sent to the subject's last known address or general practitioner and a copy of this letter should be maintained in the subject's hospital records.

Note: If a subject missed one or more of the scheduled follow-up visits (inclusive of the assigned visit windows), this will be considered as a missed visit. The subject may therefore still return for subsequent follow-up visits and will not be withdrawn from the study.

If a subject withdraws from the clinical study, the site will record the subject's reasons for withdrawal, on a Withdrawal CRF.

The status of the subject's condition should be documented at the time of withdrawal on any ongoing adverse event forms.

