**Table 3: Data Collection Overview**

Visit Activity or Information Collected	Initial Data Collection			Follow-Up Data Collection					
	Baseline	Procedure	Discharge	30-Day	1 Year	2 Year	3 Year	4 Year	5 Year
Demographics	X								
Medical History	X								
Lab measurements*	X			X					
Clinical Assessment with physical exam ^			X	X	X	X	X	X	X
Cardiovascular Medications (examples: cardiac medications and blood thinners)	X			X	X	X	X	X	X
NYHA Classification β	X			X	X	X	X	X	X
Transthoracic Echocardiography (TTE) or Transesophageal Echocardiography (TEE) γ	X		X	X	X	X	X	X	X
Procedure details		X							
Adverse Events, Device Deficiency, and Withdrawal Σ		X	X	X	X	X	X	X	X
Reintervention Procedure (if applicable)			X	X	X	X	X	X	X
Protocol Deviations related to informed consent process or inclusion/exclusion criteria, or safety reporting requirements (if applicable)	X	X	X	X	X	X	X	X	X

\*Blood tests that are standard of care; βNYHA will be determined from signs and symptoms observed attributed to heart function and can be calculated from medical records. ^Clinical assessment will assess general health and information on any new diagnostics, treatments, or tests since the last visit. ΣIf applicable; γEchocardiograms submitted to the Echo Core Lab should be imaging medium but may be provided as a report if imaging is not available to submit to the core lab.

Note: Neurologic assessments will be collected for any neurologic event (if applicable) and may be assessed from available medical records.

In the event that more than 1 echocardiogram or required data point is performed and available within a specific study data collection timepoint, the data closest to the study timepoints will be used for the primary analysis. However, all available data should be collected in additional applicable CRFs. Additional echocardiograms should be submitted to the echocardiogram core lab for analysis. Data may be collected based on availability from SOC and protocol deviations for out of window/missed visit or out of window/missed data will not be required.

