#### **9.4 Subject Study Completion**

Subject participation in the study will conclude when:

1. The subject completes the 5-year data collection time point.
2. When consent is withdrawn (by the subject or legal authorized representative).
3. When the subject is deceased at the time of enrollment or dies during the study, their study completion will occur after their last study follow-up was available, including details of what led up to death and the cause of death.
4. When the subject is lost to follow-up, their study completion will occur after their last study follow-up.
5. For subject's where the Portico delivery system entered their body but was not successfully implanted, they will complete the study after 30 days from the attempted procedure.

Upon completion of subject participation in this data-collection study, the subject will continue to receive follow-up as per standard of care.

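### Section 8.2 gives conflicting rules for loss to follow-up; a site that uses the one-missed-visit rule can stop collecting events too early, mainly for the descriptive annual rates through 5 years

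*Protocol*

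**What the plan says.** Protocol section 8.2 addresses the same subject in three places.

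- **Third paragraph.** It applies when the subject cannot be reached and the medical records are insufficient to judge status. The site must try the subject and the local or referring physician, with "at least two attempts of telephone contact on separate dates, and a registered letter before considering the subject lost-to-follow-up".
- **Bullets under early termination.** The list opens with "Reasons for early termination include, but are not limited to", and its second item is loss to follow-up. The status applies "after one missed visit, and a minimum of two phone calls from the investigational site to the subject" or a listed contact. The next bullet adds an ordinary letter, to the last known address or the general practitioner, if the two calls fail.
- **Note.** A subject who "missed one or more of the scheduled follow-up visits (inclusive of the assigned visit windows), this will be considered as a missed visit". It continues: "The subject may therefore still return for subsequent follow-up visits and will not be withdrawn from the study".

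The status has consequences elsewhere. Protocol section 9.4 item 4 lists it among the events that conclude participation: "When the subject is lost to follow-up, their study completion will occur after their last study follow-up". Section 11.6 runs safety surveillance until the last follow-up visit, the end of participation or withdrawal. Section 5.3 item 3 nevertheless asks for death, cardiovascular death, stroke and TIA rates annually through 5 years, and section 8.3 expects data over that period.

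**The concern.** A subject with one missed visit and two calls made meets the bullet and is terminated early. The same subject is covered by the Note and is not withdrawn. Under the third paragraph the status is not yet available, because no record review or registered letter has taken place. Sites may reasonably choose differently.

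The choice decides whether event collection continues. The study relies on standard-of-care records, and section 9 allows collection from records and by phone, mail or email, so an absent clinic visit is not in itself a reason to stop. Different practice between sites may also go unseen. The Table 3 notes require no deviation for missed visits, and section 14.6 limits reportable deviations to consent, eligibility and safety reporting.

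The SAP does not repair this. Section 2.2.3 censors event-free subjects at the time of analysis and gives no last-contact date for lost subjects; section 2.8 plans no imputation. Read literally, time during which nobody was looking for events would count as event-free follow-up, which pushes event rates down.

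**Working it through.** The plan states no dropout, missed-visit or failed-contact rate, so there is no figure to reproduce. The check is mainly a comparison of text.

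**1. The three rules side by side**

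| Feature | Bullet | Third paragraph | Note |
|---|---|---|---|
| Trigger | One missed visit plus at least two calls | Subject unreachable and records insufficient | One or more missed visits |
| Must the calls fail? | Not stated in the bullet; the next bullet covers failed calls | Yes, by context | Calls not mentioned |
| Separate dates for calls | Not stated | Required | Not applicable |
| Letter | Ordinary, after the calls fail | Registered, before the status | Not applicable |
| Result | Lost to follow-up, an early termination | Lost to follow-up | Stays in the study |

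The bullet and the third paragraph differ in threshold and in order: one places the letter after the status, the other before it. The bullet and the Note differ in result for any subject who missed a visit and was called.

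**2. Consequence**

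Status assigned (8.2) → participation concludes (9.4 item 4) → safety surveillance ends (11.6) → later events need not be collected, although they are wanted through 5 years (5.3 item 3).

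**3. Which follow-up is exposed**

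Index procedures precede consent, and deceased patients may be enrolled. Protocol section 12.7 and SAP section 2.8 expect most subjects to have at least 1 year of follow-up. Only timepoints still outstanding after enrolment can trigger the bullet; a visit already in the record cannot. The exposure therefore lies mainly in the later annual rates.

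**4. Illustration under assumptions**

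Let q be the chance that the bullet is triggered at an outstanding visit, and k the number of outstanding visits that precede the period of interest. Visits are taken as independent and deaths are ignored. Out of N = 100 (the maximum primary population, SAP section 1.3), the number still under surveillance is 100 × (1 − q)^k.

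| Assumed q | k = 0 | k = 1 | k = 2 | k = 5 |
|---|---|---|---|---|
| 2% | 100 | 98 | 96 | 90 |
| 5% | 100 | 95 | 90 | 77 |
| 10% | 100 | 90 | 81 | 59 |

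For example, 100 × 0.95^5 = 77. The k = 5 column means that the 30-day visit and years 1 to 4 all lay ahead at enrolment, which is the extreme case in a retrospective study. Neither q nor k is given in the documents. The table shows only that the answer could run from nothing to substantial. It counts subjects closed, not events lost.

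**The case against.** The strongest reply is that section 8.2 can be read as a whole. The third paragraph sets a mandatory floor. The bullet names a minimum and sits under an instruction to make all reasonable efforts. The Note covers a missed visit as such, while loss to follow-up means a missed visit plus failed contact. Protocol section 12.4 and SAP section 2.6 list the two statuses separately, which supports this reading. Calls may go to a listed contact and the letter to the general practitioner, so many deaths would come to light. A site that overlooked an event already in the hospital record would also be ignoring the record review in the third paragraph.

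Much of this stands. The harmonised reading is sensible and is probably what was meant, but the text does not state it. The bullet itself does not require the calls to fail, and the Note makes no exception for subjects who were called. Even if that is granted, the bullet and the third paragraph still differ on record review, separate dates and the letter.

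A reader might also infer that the 1-year performance endpoint is seriously compromised, or that a definite share of subjects and deaths will be missed. The documents do not support either. The retrospective design largely protects the 1-year result, and no source is given for any rate that such a count would need. Selective loss of frailer patients is plausible, but the documents do not show it.

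**Conclusion.** The conflict is real and should be corrected. Applied as written, the bullet lets a site end participation, and with it event reporting, on weaker grounds than the same section requires elsewhere.

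The consequence is bounded. It concerns follow-up outstanding after enrolment, and so mainly the annual rates through 5 years, which are descriptive. No hypothesis is tested on either primary endpoint (SAP section 2.10). The effect on the 1-year Kaplan-Meier estimate is limited, although the missing last-contact censoring date is relevant there too. The size of the effect cannot be derived from the documents; the illustration rests wholly on assumed values of q and k. The conclusion about the text needs no assumption beyond a site taking the bullet at its word.

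**What to change.** 1. In Protocol section 8.2, delete the one-missed-visit bullet and keep the third paragraph as the single definition of loss to follow-up.
2. State that a missed visit alone is not loss to follow-up, and that available records are still checked at later timepoints, within the consent given.
3. Cross-refer section 9.4 item 4 to that definition.
4. Record the last date known alive and event-free. In SAP section 2.2.3, use it as the Kaplan-Meier censoring date for lost subjects in place of the time of analysis.

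The status should not be held back until study closure. The 1-year data-lock rule (Protocol section 12.4, SAP section 2.6) refers to loss to follow-up before 1 year, and SAP section 3.3 summarises early termination at each scheduled visit, so both need the status earlier.

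The cost is a wording change in both documents, one recorded date, and a little extra site time to re-check records. No new visit or procedure is needed.

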### 8.3 Total Expected Study Duration

It is anticipated that all subject data would be collected from the Portico ViV procedure and through the following 5 years post-procedure.

## 9 DATA COLLECTION AND EVALUATION OF ENDPOINTS

The Principal Investigator is responsible for ensuring all study data is collected as required per the protocol scheduled time points. In addition to accessing the subject's medical records, data collection may also occur remotely by phone contact, mail, in-person, or through email. The clinical study will be conducted in accordance with the protocol. All parties participating in the conduct of the study will be qualified by education, training and/or experience to perform their tasks. This training will be documented appropriately. The data collection elements required for each follow-up are listed below and in **Table 3** below.

### 9.1 Baseline

The following baseline (pre-ViV implant procedure) data will be collected from medical records for all enrolled subjects:

1. Medical History
2. Demographics
3. Cardiovascular medications
4. New York Heart Association (NYHA) Classification (based on symptoms of any limitations)
5. Echocardiography to include comprehensive transthoracic (TTE) or transesophageal (TEE) 2D echocardiogram, including, at minimum, assessment of aortic valve gradients (mean gradient, peak jet velocity, or doppler velocity index (DVI), aortic valve area (AVA), indexed effective orifice area (EOA), indices, degree of regurgitation, cardiac output and cardiac index, left ventricle systolic function (global and segmental).  
*For all data-collection timepoints, echocardiogram reports may be acceptable if imaging study is not available to be submitted to Abbott.*
6. Lab Measurements per SOC (including CBC, Platelet count, BUN, creatinine and/or estimated GFR)
7. Protocol deviations related to informed consent process or, inclusion/exclusion criteria (if applicable)

### 9.2 Procedure

The following data will be collected from the medical records of the ViV implant procedure:

1. Vascular access, deployment, final valve placement, performance and closure data collection
2. Other product utilization (e.g. introducer sheaths, guide wires, balloon catheters)
3. Cardiac rhythm and any rhythm changes throughout the duration of the procedure
4. Procedural information (e.g. number of valves used, cerebral protection device use, fluoroscopy time, balloon dilatation used, stent size, implant depth, final disposition of the subject, etc.)
5. Adverse events and protocol deviations related to safety reporting (if applicable)

All the required information must be recorded on the applicable CRF.

### 9.3 Follow-up Data Collection

#### 9.3.1 Discharge [REDACTED]

The discharge data-collection will be from hospital discharge or up to 7 days after the procedure, whichever occurs first. If the subject was discharged over the weekend, the data collection for discharge may be based on the last weekday prior to discharge. The discharge data will be collected from medical records and includes:

1. Clinical assessment with physical exam
2. Echocardiogram (within the first 48 hours post-procedure), including parameters noted above in Baseline.
3. If applicable, reinterventions procedure details (eg. Surgery or TAVR)
4. Adverse events and protocol deviations related to safety reporting (if applicable)

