**Figure 2: Study Flow Chart**

\*Echocardiogram imaging to include comprehensive TTE or TEE 2D echocardiogram, including, at minimum, assessment of aortic valve gradients (mean gradient, peak jet velocity, or doppler velocity index (DVI), aortic valve area (AVA), indexed effective orifice area (EOA), indices, degree of regurgitation- paravalvular leak (PVL), cardiac output and cardiac index, left ventricle systolic function (global and segmental). Echocardiogram imaging studies must be submitted to Abbott when available. If not available, echocardiogram imaging reports may be acceptable.

\*\*Including CBC, Platelet count, BUN, creatinine and/or estimated GFR

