### **5 ENDPOINTS**

#### **5.1 Primary Safety Endpoint**

Composite of all-cause mortality, disabling stroke, life threatening bleeding requiring blood transfusion, acute kidney injury (AKI) requiring dialysis, and major vascular complications at 30 days.

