###### **2. Evaluation of adverse event rates**

###### At 30 days and one year:

- All-cause mortality
- Cardiovascular-related mortality
- All Stroke (by severity)
- Transient Ischemic Attacks (TIA)
- Myocardial infarction (MI)
- New pacemaker implant (PPI)
- Coronary obstruction

At 30 days:

- Minor, Major, and Life-threatening bleeding
- Major vascular, major non-vascular access-related, or cardiac structure complication
- Acute Kidney Injury (AKI) stages 1-4

3. Evaluation of adverse event rates annually through 5 years:

- All-cause mortality
- Cardiovascular-related mortality
- All Stroke (by severity)
- TIA

The following will be collected if standard of care or if available:

4. Echocardiographic assessment of valve performance at discharge, 30 days, 1 year, and annually through 5 years including:

- Transvalvular mean gradient
- Indexed Effective orifice area (iEOA)
- Doppler velocity index (DVI)
- Aortic Valve Area (AVA)
- Non-structural valve dysfunction:
  - Prosthetic patient mismatch (PPM) per body mass index (BMI)
  - Degree of aortic valve regurgitation (transvalvular and paravalvular leak (PVL)) as none/trace, mild, mild-moderate, moderate, moderate/severe, or severe per VARC-3; and per VARC-2 none/trace, mild, moderate, or severe).

5. Valve Integrity at 1 year and annually through 5 years as assessed by:

- Structural Valve Deterioration (SVD) (by hemodynamic valve deterioration (HVD) stages 1-3 per VARC-3)

Confirmed intrinsic permanent changes to the prosthetic valve, including:

- Wear and tear
- Leaflet disruption
- Flail leaflet
- Leaflet fibrosis and/or calcification
- Strut fracture or deformation

- Non-structural Valve Dysfunction other than PVL and PPM (HVD stages 1-3 per VARC-3)

Any abnormality not intrinsic to the prosthetic valve resulting in valve dysfunction other than PVL and PPM, including:

- Leaflet entrapment by pannus or tissue
- Inappropriate positioning or sizing
- embolization

- Clinically Significant Thrombosis

Meeting either of the following criteria:

- Clinical sequelae of thromboembolic event or worsening AS/transvalvular AR and HVD Stage 2-3 or confirmatory imaging of thrombosis

Or

- In the absence of clinical sequelae, both HVD Stage 3 and confirmatory imaging

- Endocarditis (by HVD stages 1-3 per VARC-3)

Meeting at least one of the following criteria:

- Fulfilment of the Duke endocarditis criteria

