#### 9.3.2 30-Day Data Collection [REDACTED]

The following data collection will occur at 30 days post index procedure:

1. Clinical assessment with physical exam
2. NYHA classification (based on symptoms of any limitations)
3. Echocardiogram, including parameters noted above in Baseline.
4. If applicable, reintervention procedure details
5. Lab Measurements (CBC, Platelet count, and Creatinine)
6. Cardiovascular medications
7. Adverse events and protocol deviations related to safety reporting (if applicable)

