**The List of Reportable Events include:**

1. Endpoint VARC-2 and VARC-3 events:
  - Death (all-cause and cardiovascular-related)
  - Myocardial Infarction
  - Major Vascular complications
  - Major non-vascular access-related complications
  - Stroke/TIA
  - Bleeding
  - Acute kidney Injury
  - New permanent pacemaker implantation
  - Coronary obstruction
  - Cardiac structural complication
  - Portico valve endocarditis
  - Portico valve thrombosis
  - Need for reintervention (conversion to surgery or repeat TAVR ViV)
  - Portico valve structural deterioration
2. All non-serious device or procedure related Adverse Events.
3. All Serious Adverse Events (SAEs) regardless of device or procedure relationship
4. All Cardiovascular and Neurological events regardless of device or procedure relationship
5. Device Deficiencies (DDs)/Device Malfunctions

Sites must report SAEs and DDs to the Sponsor no later than 3 calendar days from the day the site personnel became aware of the event or as per the investigative site's local requirements, if the requirement is more stringent than those outlined.

Sites must record the date the study staff became aware that the event met the criteria of an SAE in the source document. The Investigator will further report the SAE to the local EC according to the institution's EC reporting requirements.

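### Section 9 and Table 3 list no creatinine between baseline and day 30, so the descriptive AKI stage 1-3 rate may read low; separately, Section 11.6 starts adverse-event collection at enrolment

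*Protocol*

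**What the plan says.** **Schedule.** The opening paragraph of Protocol Section 9 points to the lists in that section and to Table 3 for the data elements required at each follow-up. Labs appear at baseline (9.1 item 6) and at 30 days (9.3.2 item 5: "Lab Measurements (CBC, Platelet count, and Creatinine"). The procedure list (9.2) names none. The discharge list (9.3.1: "The discharge data will be collected from medical records and includes") has four items: clinical assessment, echocardiogram, reintervention details, and adverse events with deviations. Discharge data run to hospital discharge or "up to 7 days after the procedure, whichever occurs first". Table 3 marks labs under Baseline and 30-Day only.

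**Endpoints.** The 30-day descriptive endpoints (Protocol 5.3, repeated in SAP 1.4.3) include "Acute Kidney Injury (AKI) stages 1-4". The primary safety composite (5.1) takes only the severe end: "life threatening bleeding requiring blood transfusion, acute kidney injury (AKI) requiring dialysis", together with death, disabling stroke and major vascular complications.

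**Other capture routes.** Section 11.6 makes "Endpoint VARC-2 and VARC-3 events" reportable, and that list includes AKI, bleeding and stroke. The Synopsis says the CEC will request source documents. A Table 3 footnote adds: "Clinical assessment will assess general health and information on any new diagnostics, treatments, or tests since the last visit". A further note under Table 3 collects neurologic assessments for any neurologic event.

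**Start of adverse-event collection.** Section 11.6 begins surveillance once enrolment requirements are met and ties collection of adverse-event data to that period. Section 8.1 makes consent one of those requirements.

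**The concern.** AKI stages 1-3 are laboratory diagnoses. If the listed data contain no creatinine from the days when they are defined, the rate depends on a site having recognised and reported each case. Recognition can differ between sites, and the error runs one way: unlabelled cases count as no event. Protocol 12.7 and SAP 2.8 plan no imputation, and the text under Table 3 waives deviations for missed data, so nothing would flag the gap. In a single-arm registry there is no comparator to absorb such an undercount.

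The second matter is wording. In a retrospective study consent follows the procedure. A collection period that begins at enrolment, taken at its word, can miss the interval in which the 30-day primary safety endpoint is observed.

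**Working it through.** The plan states no figure on this point to reproduce. The check compares schedule with definitions, then illustrates the possible size.

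**1. Listed labs against the AKI windows**

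| Timepoint | Labs listed? | Inside 48 h after procedure | Inside 7 days after procedure |
|---|---|---|---|
| Baseline (9.1) | yes | no (before) | no (before) |
| Procedure (9.2) | no | - | - |
| Discharge (9.3.1) | no | - | - |
| 30-Day (9.3.2) | yes | no | no |

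Table 3 has 9 columns (Baseline, Procedure, Discharge, 30-Day, Years 1 to 5); labs are marked in 2. Listed post-procedure labs inside the windows: 0 for 48 hours and 0 for 7 days. The 30-day visit window is redacted, but it would have to open 30 - 7 = 23 days early for its labs to reach the 7-day window.

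**2. What Appendix B needs.** VARC-2 AKI uses creatinine change up to 48 hours, or urine output. VARC-3 bases stages 1-3 on creatinine, within 7 days or (the 0.3 mg/dL criterion) 48 hours; one stage 3 criterion carries no stated window. Stage 4 is renal replacement. So 3 of the 4 VARC-3 stages rest on creatinine, mainly from days without a listed lab.

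**3. Whether event reporting fills the gap.** Section 11.6 says an abnormal non-cardiac lab value is not an adverse event unless the investigator finds it clinically significant, or it led to intervention or withdrawal. A 0.3 mg/dL rise within 48 hours meets VARC-3 stage 1, yet a site applying that rule may report nothing.

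**4. Size.** With N = 100 (the maximum in SAP 1.3), one missed case lowers a 30-day proportion by 1/100 = 1.0 percentage point. The documents give no AKI rate and no capture rate, so what follows is illustration with assumed values. Let p be the true stage 1-3 rate and s the share captured; the expected reported rate is p × s. Coverage is the sum of Bin(x; 100, p × s) over those x whose exact 95% Clopper-Pearson interval contains p.

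| True p | s = 100% | s = 75% | s = 50% |
|---|---|---|---|
| 5% | 98.3% | 97.7% | 92.0% |
| 10% | 95.6% | 87.6% | 56.4% |
| 15% | 96.6% | 88.6% | 47.8% |
| 20% | 96.7% | 83.6% | 29.7% |

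Example: 10 true cases give 10.0% (4.9 to 17.6%); if 5 are captured, the report reads 5.0% (1.6 to 11.3%).

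**5. Primary composites.** Death and dialysis do not depend on the missing labs. The bleeding component requires transfusion, so a haemoglobin drop alone cannot count. Of the 4 VARC-2 criteria for life-threatening bleeding, 1 rests on haemoglobin or units.

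**6. Section 11.6 beside the rest**

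- Section 11.6 with 8.1: collection starts when enrolment requirements, including consent, are met.
- Section 8.3: data run from the procedure for five years.
- Sections 9.2 and 9.3.1, and Table 3: adverse events are collected at procedure and discharge.
- Section 9.4 item 3: for subjects deceased at enrolment, details of the death are expected.
- Note in the Section 11.6 timelines table: only SAEs before the procedure are exempt.

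Read literally, Section 11.6 omits the whole 30-day window for anyone consented after day 30, and leaves an empty period for a subject already deceased at enrolment.

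**The case against.** **The governing schedule is not visible.** SAP 1.3 refers both arms to Figure 2 for timepoints and data requirements. That figure is not shown, though its footnote carries a lab panel ("Including CBC, Platelet count, BUN, creatinine and/or estimated GFR"). This stands as a limit: if Figure 2 marks labs at discharge, the point becomes a mismatch between Figure 2 and Table 3.

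**Other routes exist.** The clinical-assessment footnote takes in tests since the previous visit, and Protocol 15.4 provides for source review and centralised checks for missing data. These could recover values, but none names creatinine or the 48-hour and 7-day windows.

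**The fix cannot make practice uniform.** True: sites that measured creatinine more often will find more AKI. AKI stages 1-3 are also descriptive, and SAP 2.10 specifies no hypothesis test. This limits the weight of the point.

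**Stronger readings that a reader might infer.**

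- *The primary composites are materially understated.* Not supported. Bleeding and stroke are reportable and reviewed by the CEC from source. Appendix B (VARC-3 bleeding, note a) already asks for transfusion timing and number, even without overt bleeding.
- *Disabling stroke cannot be classified.* Not supported. Neurologic assessments are collected for any neurologic event. What remains is that the note does not name the mRS, and that subjects with an unsuccessful implant complete at 30 days (9.4 item 5, 11.6.1), at least 90 - 30 = 60 days before a 90-day mRS if exit is on day 30.
- *Section 11.6 flatly contradicts its own note, or events before consent will be dropped.* Too strong. A period starting at enrolment makes the note redundant; the conflict is by implication, because exempting only pre-procedure SAEs makes sense only if collection runs from the procedure. Other sections show that intent.

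**Conclusion.** The point holds for creatinine-graded AKI. A site following Section 9 and Table 3 as written need not record any creatinine from the days when stages 1-3 are defined, so the descriptive 30-day rate may read low. The actual loss cannot be derived: the per-case effect is 1.0 percentage point at N = 100, and the coverage figures rest on assumed rates and capture shares. Any effect on the primary composites is minor.

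The Section 11.6 wording is a separate internal inconsistency that must be reconciled, since its literal period can exclude the primary safety window.

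The conclusion covers the listed schedule only. It does not show that the values go uncollected, because Figure 2 and the CRFs could not be checked. Both matters are worth correcting; neither invalidates the study.

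**What to change.** 1. Add to Section 9, Table 3 and the CRF, abstracted from existing records where available: peak creatinine to 48 hours and to 7 days after the procedure, whether or not the subject has been discharged. Carry the transfusion data that Appendix B already requests into the same schedule, and check that Figure 2 agrees.
2. Reconcile Section 11.6 with 8.3, 9.2, 9.3.1, 9.4 item 3, Table 3 and its own note, so that retrospective adverse-event collection covers the period from the index procedure for every enrolled subject, including those deceased at enrolment.
3. Optional and minor: name the pre-stroke mRS and the mRS nearest 90 days in the neurologic-assessment note under Table 3, and reconcile this with the 30-day completion in 9.4 item 5 and 11.6.1.

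The cost is a few CRF fields and some reworded sentences, with no new tests or visits. The downsides are slightly more chart abstraction, some values that standard-of-care records will not hold, and possibly a higher reported AKI rate.
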